7.0 STUDY PROCEDURES

7.1 Data to be collected prior to start of intervention

1. Patient demographics at time of ICU admission (age, gender, weight, height, BMI, race, ethnicity, date of birth)
2. Past medical and surgical history as recorded in the latest admission on the electronic patient record (EPR)
3. Date and reason for hospital admission, and source of admission.
4. Date, time and reason for ICU admission including any concomitant problems
5. Date and time of septic shock onset (start time defined by criteria for septic shock, vital information that should be carefully determined, since “Timely delivery of EMR before Mitochondrial Respiration slows down” is the crux of the study)
6. Suspected source of sepsis
7. Presence or absence of oncologic disease, state and diagnosis of metastatic disease at time of ICU admission if known
8. Nutritional status based on the assessment by the dietitian in the ICU (this may be recorded after onset of intervention if not available initially) including any history of weight loss or signs of malnutrition
9. Patient vital signs and hemodynamic status

10. Supplementary oxygen and NIV/intubation status
11. Baseline CBC, blood chemistry panel, coagulation screen and ABG (baseline defined as within 12 hours of randomization for venous tests and 4 hours for ABG – if these have not been done we will send additional baseline investigations)
12. Any relevant microbiology results (blood, urine cultures, wound cultures, serum microbiological tests) and pertinent imaging results (radiology reports only – images not to be recorded)
13. Admission Sequential Organ Failure Assessment (SOFA) score
14. Pregnancy status - women of child bearing potential (defined as women <60 who have not been postmenopausal for at least one year or have not had a hysterectomy) will have either a serum or urine B-HCG test to exclude pregnancy. A positive pregnancy test is grounds for exclusion from the study. This will have already been undertaken as a part of screening if the above criteria are met.

7.2 Data to be collected prospectively

Vital signs including blood pressure, heart rate, respiratory rate, pulse oximetry, co-oximetry will be measured, as well as cardiac assessment by 2D echocardiogram. The following information will be collected prospectively if available. The order sets describe the timing and frequency of the lab draws. If clinical condition indicates, blood tests may occur more frequently at discretion of primary team. Additional tests may not necessarily be recorded. The below order sets indicate minimum frequency. *Day 0 is day of recruitment.*

Daily SOFA scores - will be generated automatically by the electronic health record if this option exists in the institution or manually with table 1 once daily.

Laboratory Data:

1. Complete Blood Count and Coagulation profile
 - a. First 24hrs after start of intervention: every 8 hours ± 120 minutes
 - b. After 24hrs of intervention: every 12 hours ± 120 minutes
2. Cultures (as ordered by primary team – *we will not specify culture requirements though at least one set of blood cultures should be taken as required by sepsis management algorithm*)
3. Liver function tests and lipase
 - a. First 24hrs after start of intervention: every 12 hours ± 120 minutes
 - b. After 24hrs of intervention: every 24 hours ± 120 minutes
4. Serum cholesterol (to be collected once daily only days 1, 3, 5)
5. Thyroid test: Thyroid function tests (to be collected once daily only days 1, 3, 5)
6. Blood chemistry panel
 - a. Includes: Albumin, BUN, Ca^{2+} , Na^+ , K^+ , Cl^- , CO_2 , Creatinine, Glucose, Phosphorus, and Gama-Glutamyl transpeptidase
 - b. First 24-hrs after start of intervention: every 4 hours ± 120 minutes (Will require VAMP System or similar blood sparing device to avoid wasting blood)
 - c. After 24-hrs of intervention: every 8 hours ± 120 minutes
7. Arterial blood gas and venous blood gas (via central venous catheter)

- a. First 24hrs after start of intervention: every 4 hours ± 120 minutes
- b. After 24hrs of intervention: every 8 hours ± 120 minutes

8. Lactic acid

- a. First 24-hrs after start of intervention: every 4 hours ± 120 minutes
- b. After 24-hrs of intervention: every 8 hours ± 120 minutes

9. Serum Cortisol once daily (morning)

10. Uric acid once daily (morning)

11. Inflammatory markers (ESR, Procalcitonin) to be collected once daily.

12. Creatinine phosphokinase (to be collected once daily only on day 1, 3, 5)

Outcome data:

- 1. Length of stay (LOS)
 - a. Time from hospital admission to admission to the ICU (Length of stay before admission to the ICU)
 - b. Length of the stay in the ICU
 - c. Length of hospital stay
- 2. Mortality
 - a. Hospital mortality
 - b. ICU mortality
 - c. 28 day mortality
 - d. 90 day mortality
- 3. Ventilator days – ventilator free days, duration of intubation (days)
- 4. Any newly documented hospital acquired infection(s)
- 5. Any acute kidney injury as defined by acute kidney injury network criteria:
 - a. An acute (within 48h) rise in serum creatinine of 0.3g/dl or more

- b. A percentage increase of serum creatinine of 50% or more
 - c. Documented oliguria <0.5 ml/kg/hr for >6 hours
 - d. Need for dialysis
 - e. Dialysis free days
- 6. Inotropic free days and duration of inotropic support (hours or days)
- 7. Vital signs and any hemodynamic monitoring (cardiac index, CVP, ScvO2) implemented will be recorded – there is no specific requirement for hemodynamic monitoring beyond arterial-line recorded MAP/BP/HR.
- 8. All patients will be followed up for up to 90 days.

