6.3 Duration of intervention

The above infusions will be started and continued for seven days unless the patient dies or is discharged from the ICU. Infusions have to be continuously maintained and not stopped for any routine investigations. If the patient is tolerating enteral tube feeds at $\geq 70\%$ of goal for a full 24 hours as determined by the ICU dietician, the intervention will be stopped (established weaning process to avoid precipitation of hypoglycemia).

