- i. Study intervention is to be stopped. Record as adverse event. Manage as per ICU protocol

f. Hypomagnesemia (Mg <1.5mg/dl)

- i. Replace as per ICU guidelines – N.B. target magnesium is ≥ 3 mg/dl in intervention group

g. Aluminum toxicity

- i. Aluminum toxicity is seen in neonates; however, this population is excluded in our study.

- ii. Patients in renal failure are at risk of bio-accumulating aluminum when solutions contain >50 micrograms/L. In this study, patients with renal failure are excluded and free amino acids only contains <25 micrograms/L.
- iii. Currently, to measure blood aluminum levels is not standard of care in a) patients not at risk of bio-cumulating the metal, b) patients receiving solutions that contain aluminum below 50 micrograms/L.
- iv. Aluminum toxicity is not an expected adverse event in this study patient population.

h. Hypophosphatemia (PO4 <1mg/dl)

- i. Additional replacement as per standard ICU guidelines

i. Hyperphosphatemia (PO4 >6.5mg/dL)

- i. Check renal function and calcium. Discuss with principal investigator. Hyperphosphatemia is not usually symptomatic and does not usually cause direct toxicity. The product of calcium x phosphate should be less or equal to 60. Record as adverse event

3. Hyper/hypoglycemia (see appendix)

For the very likely event of hyper/hypoglycemia in the EMR group we have developed an algorithm, which is a slight modification of standard ICU glucose management protocols and itself refers to ICU sliding scale insulin protocols. As glucose management is anticipated as a potential issue, monitoring of glucose is to occur at least hourly in the treatment arm. Please see appendix for detailed information on glucose management. Target glucose is 140-180mg/dl.

4. Allergic reactions (related to study components or suspected relation)

- Urticarial reaction
 - Begin antihistamine. Record as possible adverse event. Monitor patient – if EMR components suspected as the causative AND worsening reaction consider stopping solution and replace with D50 IV solution and exclude the patient from the protocol. At the same time treat the patient until reaction resolves. (Frequent glucose monitoring once solution discontinued). Contact principal investigator and follow hypersensitivity institutional protocol.
- Anaphylaxis

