8.3 Adverse Events and Serious Adverse Events

- **An adverse event (AE)** is generally defined as any unfavorable and unintended diagnosis, symptom, sign (including an abnormal laboratory finding), syndrome or disease which either occurs during the study, having been absent at baseline, or if present at baseline, appears to worsen. Adverse events have to be recorded regardless of their relationship to the study intervention.

- **A serious adverse event (SAE)** is generally defined as any untoward medical occurrence that results in death or that is life threatening, requires inpatient hospitalization or prolongation of existing hospitalization, results in persistent or significant disability/incapacity, or in a congenital anomaly.

As discussed in 8.1, the study solution is not a novel pharmaceutical product and is unlikely to cause any significant adverse event. Theoretical complications of the solution are common problems in critical care units. Vigilance and close monitoring, together with high staffing levels in ICU reduce the potential for harm. Bearing these facts in mind, there are only three scenarios, which will be reported as serious adverse events in the EMR group:

- 1) **Anaphylaxis (to study components)**
- 2) **Arrhythmia secondary to electrolyte disturbance**
- 3) **Hypoglycemia (<70mg/dL)**

These will be monitored for via electronic medical records. All suspected adverse reactions and above adverse events must be reported by unit staff or research team to the principle investigator who will provide within 1 week such reports to the Institutional Review Board. We estimate that adverse reactions are not very likely, as this study lacks novel pharmaceutical agents. Patient safety has been thoroughly considered by the study chairs.

Only the adverse events and serious adverse events that happen within the 7 days of enrollment will be logged and reported to the IRB.

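### Glucose is sampled and hypoglycemia named as an SAE differently in the two arms, and unscheduled results need not be stored, so the objective 4 comparison of glucose and electrolyte events is open to ascertainment bias.

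*Combined protocol and SAP*

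**What the plan says.** Section 7.2 (Data to be collected prospectively) lists glucose only within the blood chemistry panel, item 6. The frequencies are "First 24-hrs after start of intervention: every 4 hours ± 120 minutes" and "After 24-hrs of intervention: every 8 hours ± 120 minutes". The section calls this a floor: "The below order sets indicate minimum frequency". On draws beyond it, the section says "If clinical condition indicates, blood tests may occur more frequently at discretion of primary team", and then "Additional tests may not necessarily be recorded".

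Section 8.2, under hyper/hypoglycemia, treats glucose excursions on EMR as very likely and states that "monitoring of glucose is to occur at least hourly in the treatment arm". It sets no corresponding frequency for standard care.

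Section 8.3 limits SAE reporting to three scenarios, all specified for the EMR group. The third is "Hypoglycemia (<70mg/dL", that is, glucose under 70 mg/dL. These are looked for in the electronic medical record, must be reported by unit staff or the research team, and are logged for seven days from enrollment. Section 8.3 also defines an adverse event broadly enough to include abnormal laboratory results, and requires AEs to be recorded whatever their relation to treatment. That duty is not limited to one arm.

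Objective 4 (section 1.2) is to describe adverse effects in the two groups and so characterize safety.

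**The concern.** Objective 4 sets the safety of the two arms side by side. For glucose, the plan looks much harder in one arm than in the other, and it gives a low value SAE status in that arm only. The trial is unblinded, so whoever decides what to report knows the assignment. With equal true rates, the arm sampled more often tends to show more events. An apparent excess on EMR could therefore be partly an artefact of monitoring, and a real excess could be dismissed as one.

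Stored results would let the analyst separate the two explanations by restricting both arms to the same sampling times. The section 7.2 wording does not secure the full set of values. For electrolytes the scheduled panel carries no arm distinction, but extra draws follow clinical judgement, and several section 8.2 instructions are written around the study infusion. For example, potassium at or above 5.5 mmol/L is tied to EMR I being infused, and magnesium above 4 mg/dL to stopping the intervention.

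**Working it through.** The plan states no figure on this point to reproduce, so the check is a count followed by a comparison of the two arms.

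**Inputs**
- Chemistry panel (section 7.2): every 4 h in the first 24 h, every 8 h afterwards.
- Glucose on EMR (section 8.2): at least every hour.
- Duration (section 6.3): "The above infusions will be started and continued for seven days unless the patient dies or is discharged from the ICU". Seven days is therefore the maximum, and early weaning shortens it.
- Assumption: the section 7.2 schedule applies to both arms. The text ties it to the start of intervention but names no arm.

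**Counts over seven days**
- Scheduled panels: 24/4 + 6 × (24/8) = 6 + 18 = 24.
- Hourly glucose on EMR: 24 × 7 = 168.
- Share of EMR glucose values on the schedule: 24/168 = 14.3% (6/24 = 25% on day one, 3/24 = 12.5% on each later day).
- EMR values outside the section 7.2 list: 168 − 24 = 144, or 85.7%.

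**The arms side by side**

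| | SC + EMR | SC |
|---|---|---|
| Minimum scheduled panels | 24 | 24 |
| Required glucose values | at least 168 | 24 |
| Glucose < 70 mg/dL a named SAE | yes | no |
| General AE recording duty | yes | yes |
| Unscheduled results must be stored | no visible rule | no visible rule |

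**Sampling ratio.** At the required minimum it is 168/24 = 7. Actual usual-care sampling on standard care is not given. If it were every 4 h throughout, there would be 42 values and a ratio of 4; every 2 h, 84 values and a ratio of 2; hourly, a ratio of 1. The plausible range is therefore 1 to 7.

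**What unequal sampling could do to detection.** Assume a low lasting L hours, starting at a random time relative to the draws, and a standard-care arm tested only at the minimum schedule. The chance that a scheduled draw falls inside it is min(1, L/4) on day one and min(1, L/8) later. The seven-day average is [min(1, L/4) + 6 × min(1, L/8)]/7. Hourly sampling catches any low of an hour or more.

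| L (assumed) | SC, minimum schedule | EMR, hourly | Apparent ratio at equal true rates |
|---|---|---|---|
| 1 h | 14.3% | 100% | 7 |
| 2 h | 28.6% | 100% | 3.5 |
| 4 h | 57.1% | 100% | 1.75 |

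These are outer bounds. Any extra testing on standard care moves the ratio towards 1.

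**Electrolytes.** Potassium, sodium, phosphorus and creatinine are in the section 7.2 panel, so a common-schedule comparison is possible. Magnesium is not in that panel, although section 8.2 uses magnesium above 4 mg/dL as a recorded event and section 6.2 sets a magnesium target for the EMR arm.

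**The case against.** The strongest reply is that section 7.2 excludes nothing. Its wording is permissive and follows a sentence about discretionary draws. Hourly glucose on EMR is a protocol requirement, so it need not count as an additional test at all. Section 8.3 then provides a separate route for hypoglycemia, and section 8.2 tells staff to record several electrolyte excursions as AEs, with no restriction to scheduled samples. Results stay in the source record, and section 11.4.4 provides for review of inpatient electronic records. The appendix glucose algorithm and the data collection form mentioned in section 11.1 are not visible, and either might list the hourly values.

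Most of this stands, and it rules out some stronger readings.

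- A reader might infer that the dataset cannot show hypoglycemia on EMR. Section 8.3 contradicts that: a low hourly value is reportable whether or not it appears in the section 7.2 list.
- A reader might take the 85.7% (87.5% after day one) as the share of values or events lost. It is only the share of glucose values outside a routine listing.
- A reader might infer that seven in eight EMR lows are missed. That would hold only if events were found solely from scheduled panels and lasted about an hour, and section 8.3 does not work that way.
- A reader might infer that the 25% rule in section 10.6 fails. That rule concerns the EMR arm alone and counts severe or untreatable events, which need clinical judgement, so the difference between arms does not enter it.

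The reply does not remove the asymmetry. Reported events are not stored values, the hourly requirement and the named SAE belong to one arm, and the general AE duty cannot pick up a low value that was never measured. If hourly values are not additional tests, the visible text still does not list them as study data.

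**Conclusion.** The point holds as a problem of unequal ascertainment between arms, not as a failure to capture EMR events. Followed as written, the plan gives objective 4 a glucose comparison based on at least 168 values in one arm and a required minimum of 24 in the other, with SAE status for hypoglycemia in one arm only, and no visible rule that keeps the values needed to check it. For electrolytes the asymmetry is weaker: it lies in discretionary draws and in recording instructions tied to the infusion.

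The size of any bias cannot be read from the documents. The sevenfold sampling ratio assumes a full seven-day infusion and no standard-care glucose testing beyond the schedule; heavier usual-care testing would reduce it, possibly to 1. The likely direction for glucose is to overstate events on EMR relative to standard care. The primary endpoint is unaffected. The change should be made because it is cheap and the comparison is a stated objective.

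**What to change.** Replace the section 7.2 sentence with a rule such as:

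> All glucose (laboratory and point-of-care), potassium, sodium, magnesium, phosphorus and creatinine results obtained on days 0 to 7 are exported from the electronic record for both arms, whether scheduled or not.

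Then add to section 10.5:

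1. Glucose and electrolyte events for objective 4 are counted with the same numerical thresholds in both arms. This is a counting rule and changes no clinical management. Where the visible text gives no threshold, as for hyperglycemia, the sponsor should state one for both arms.
2. Between-arm event rates are reported twice: on the common scheduled samples, where sampling is equal, and on all samples, with the number of samples per patient-day shown by arm. Magnesium can be reported only on all samples unless it is added to the scheduled panel.
3. The export is used to cross-check the section 10.6 events, not to replace them, because severity and untreatability cannot be read from laboratory values alone.

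The cost is a small export and analysis task. The plan already draws on the electronic record in sections 6.4 and 8.3, and section 11.2 says the database can import external data. No blood draws are added.

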5.0 SELECTION AND ENROLLMENT OF PARTICIPANTS

5.1 Inclusion Criteria

- Adult patients aged 18 years old or older
- Admitted to the adult medical intensive care unit (MICU)
- Diagnosis of Septic Shock within 12 hours of ICU admission , unless the patient is already admitted to the ICU, defined as meeting criteria for sepsis in addition to the following:
 - Vasopressor therapy needed to elevate MAP \geq 65 mmHg.
 - Lactate $>$ 1 mmol/L (9 mg/dL) and/or Base excess $<$ -2 after adequate fluid resuscitation.
- Sequential Organ Failure Assessment (SOFA) score meeting the following requirements
 - Cardiovascular SOFA \geq 2
 - Total SOFA score \leq 12
- Patients meeting the mentioned inclusion criteria and not able to tolerate enteral nutrition above 70% of their estimated daily caloric need

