5.3 Study Enrollment Procedures

- A. Upon admission to the Emergency room or MICU, patients diagnosed with septic shock will be referred by the ICU attending to the designated study personnel who will then screen the patient for inclusion and exclusion criteria. The Basic Metabolic Panel (BMP) and patient medical chart history will be reviewed. If patient meets inclusion criteria (and no exclusion criteria) the patient's primary attending will be contacted for permission to enroll patient into the study. If the attending physician agrees, the patient (or if patient unable to consent, the patient's Legal Representative Power of Attorney or Next of Kin) will be approached.
- B. A discussion will be held with the next of kin and/or patient as appropriate to discuss the study procedures, possible adverse effects and research rationale. Informed consent will be mandatory and we will provide ample time to answer any questions or concerns about the protocol. A fully informed consent will be recorded in writing as per local guidance. It will be made clear to the participant and relatives that they are under no obligation to participate in the study and are free to withdraw

at any time, without giving a reason. Please see appendix for consenting material. If there is a possibility of pregnancy (defined as women <60 who have not been postmenopausal for at least one year or have not had a hysterectomy) then a serum or urine B-HCG test will be taken (with consent) prior to enrollment into the study. Refusal of pregnancy test will be considered grounds for exclusion.

The research coordinator will track all the potential candidates (patients meeting inclusion criteria) not included in the study in parallel due to logistical limitations (e.g. lack of research staff on weekends).

- C. Screening will be within 12 hours of patient being admitted to the ICU. Recruitment and initiation of study solution (where applicable) must occur both within twelve hours of the recorded onset of septic shock and admission to the MICU.

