10.0 STATISTICAL CONSIDERATIONS

10.1 Study Endpoint and Outcomes

The primary objective of this study is to assess the efficacy of administering Early Metabolic Resuscitation with Standard of Care (SC + EMR) in patients diagnosed with septic shock for reducing 28 day mortality versus using the Standard of Care alone (SC).

The primary endpoint of the study is 28-day mortality. The rationale for selecting the 28-day timeframe as the primary endpoint for comparison is that the MDACC ICU length of stay and the hospital length of stay in patients diagnosed with septic shock have wide variability (ICU LOS = Mean 9.45 ± 13.06 min: 0 max: 104, and Hospital LOS = Mean $26.4 \pm SD 26.4$ min:1, max: 242). This variability is incurred from sources that cannot be controlled. For this reason, measures such as 28-day and 90-day mortality provide more objectivity and align with outcomes described in the literature.

Secondary outcomes include ICU mortality, hospital mortality, 90-day mortality, incidence of acute kidney injury (dichotomous variable), time on cardiovascular support (continuous variable), time on ventilator (continuous variable) and length of ICU and hospital stays (continuous variables).

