10.5 Data Analyses

Descriptive statistics including the mean, standard deviation, median, and range will be used to summarize continuous variables. Frequency counts and percentages will be used to summarize categorical variables. Categorical variables, including 28 day mortality, will be compared between intervention groups using a chi-square test, or Fisher's exact tests if more appropriate. Continuous variables will be compared between intervention groups using an independent samples t-test, or Wilcoxon rank-sum test if more appropriate.

Logistic regression will be used to assess relationships between patient characteristics and binary study outcomes of interest. Continuous variables, including the time on cardiovascular support and time on ventilator, will be compared using t-tests or Wilcoxon rank-sum tests.

Time to event analyses will be conducted using Cox proportional hazards regression. For 28-day mortality, living patients will be censored after one month after the treatment was given. For overall survival, patients will be followed until time of death or date of last follow-up (maximum 6 months). Kaplan-Meier plots will be used to visually compare time to death from any cause between intervention arms followed by a log-rank test to compare survival distributions.

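### Hospital stay has no stated start point; read plainly it includes days before randomisation, which costs precision in a secondary between-arm comparison

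*Combined protocol and SAP*

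**What the plan says.** Secondary objective 3 (section 1.2) asks whether SC + EMR shortens ICU and hospital stay. Section 10.1 lists "length of ICU and hospital stays (continuous variables") among the secondary outcomes. Section 7.2 (Outcome data, item 1) collects three stay variables: "Time from hospital admission to admission to the ICU (Length of stay before admission to the ICU"), "Length of the stay in the ICU" and "Length of hospital stay". The first has defined ends; the other two have no stated start.

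The planned test is in section 10.5: "Continuous variables will be compared between intervention groups using an independent samples t-test, or Wilcoxon rank-sum test if more appropriate". Nothing there removes or adjusts for days before randomisation.

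Two passages govern how much time can pass before randomisation. Section 5.3 says recruitment and the start of study solution "must occur both within twelve hours of the recorded onset of septic shock and admission to the MICU". Section 5.1 requires shock to be diagnosed within 12 hours of ICU admission, "unless the patient is already admitted to the ICU". No section limits time in hospital before the ICU.

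**The concern.** Other time measures in the plan have an origin: 28-day mortality runs from first administration (section 1.1), and study days are numbered from recruitment (section 7.2). Stay has none. If it is counted from admission, each patient's value is the sum of a part fixed before allocation and a part that treatment could influence. The first part adds variance to an unadjusted comparison and carries no information about EMR.

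Hospital stay is the outcome exposed. Historical means in section 10.1 are 26.4 days in hospital and 9.45 days in ICU, so on average 26.4 − 9.45 = 16.95 days were spent outside the ICU. The documents do not split these into before and after, but a pre-ICU part of some size is plausible.

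Leaving the origin open also means that, in an unblinded trial, it could be settled after the data are seen.

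**Working it through.** **The plan's own figure.** No power is stated for length of stay; the only powered comparison is 28-day mortality. With the pooled chi-square formula, n per arm = [1.960·√(2·0.55·0.45) + 1.282·√(0.70·0.30 + 0.40·0.60)]² / 0.30² = 55.7, so 56. Power at 56 per arm is 90.2%. Section 10.2 reproduces, and the present point does not touch it.

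**Inputs**
- Arm size: 56 (section 10.2).
- SD of whole hospital stay: 26.4 days (section 10.1).
- SD of whole ICU stay: 13.06 days (section 10.1: "ICU LOS = Mean 9.45 ± 13.06 min: 0 max: 104").
- SD of the pre-randomisation part of hospital stay: not in the documents. Assumed at 2, 5, 10 and 15 days.
- Pre- and post-randomisation parts assumed uncorrelated.

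**Formulas**
- Variance share = SD_pre² / SD_total².
- SD_post = √(SD_total² − SD_pre²).
- Difference detectable with 80% power, two-sided 0.05 = (1.960 + 0.842) · SD · √(2/56).
- Extra patients that whole-stay counting would need for the same precision = 1/(1 − share) − 1.

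**Hospital stay.** Counted from admission: 2.802 × 26.4 × 0.1890 = 13.98 days. Counted from randomisation:

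| Assumed SD_pre (days) | Variance share | SD_post (days) | Detectable difference (days) | Power at a 13.98-day difference | Equivalent extra patients |
|---|---|---|---|---|---|
| 2 | 0.6% | 26.32 | 13.94 | 80.2% | 0.6% |
| 5 | 3.6% | 25.92 | 13.72 | 81.4% | 3.7% |
| 10 | 14.3% | 24.43 | 12.94 | 85.7% | 16.8% |
| 15 | 32.3% | 21.72 | 11.50 | 92.6% | 47.7% |

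**ICU stay under section 5.3.** Time in the MICU before the start of study solution lies between 0 and 0.5 day. A variable confined to that range has SD at most 0.25 day (half the patients at each end), or 0.5/√12 = 0.14 day if uniform. The largest possible share is 0.25²/13.06² = 0.04%. The detectable difference is 6.91 days either way.

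**ICU stay if the section 5.1 exception applies.** Assumed SD_pre of 1 / 2 / 3 / 5 days gives shares of 0.6 / 2.3 / 5.3 / 14.7%, and the detectable difference falls from 6.91 to 6.89 / 6.83 / 6.73 / 6.39 days.

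**Sensitivity to the correlation assumption.** In general, Var(post) = Var(total) − Var(pre) − 2·Cov(pre, post). A positive covariance makes the gain larger than tabulated; a negative one makes it smaller and could remove it.

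**The case against.** Several parts of the opposing case stand.

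- *The plan never says that stays are counted whole.* Correct. That is the natural reading of an undefined hospital stay, not stated text. The supportable statement is that the origin is undefined.
- *The separate pre-ICU variable is a safeguard, not a fault.* Largely correct. Section 7.2 does not say that it is added into an analysed outcome, and recording it separately makes subtraction or adjustment possible. But it is filed as an outcome although it is complete before allocation, and section 10.5 does not commit the analysis to using it.
- *Whole stay is a legitimate measure.* It is, as a description of resource use, and sections 2.6 and 3.0 cite economic burden as a motive. That supports reporting it, not making it the measure of the treatment effect.
- *The size is assumed.* Correct. At an SD of 2 days the gain is trivial. Hospital stay is also skewed (mean and SD both 26.4, minimum 1) and may be tested by Wilcoxon, so the normal approximation is only indicative.

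A reader might go further and infer three things that the documents do not support. First, that the comparison is biased or the mean difference diluted: days fixed before allocation cancel in expectation between randomised arms, and a chance imbalance is already covered by the type I error. Second, that ICU stay suffers as hospital stay does: the 12-hour rule in section 5.3 rules this out unless the section 5.1 exception is used for patients with earlier ICU days. Third, that ventilator and cardiovascular-support time carry the same loss: the documents give no spread for either, so no size can be attached.

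**Conclusion.** The point holds for hospital stay, as an avoidable loss of precision in one secondary comparison. Its size cannot be fixed from the documents: 0.6% to 32.3% of the variance over an assumed pre-randomisation SD of 2 to 15 days, or 0.04 to 2.48 days off a detectable difference of 13.98. This rests on uncorrelated parts, a normal approximation, and historical SDs from the centre's septic shock patients, who were not selected by this trial's eligibility criteria.

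For ICU stay the loss is at most 0.04% of variance under section 5.3. It could matter only through the exception in section 5.1, which section 5.3 as written does not allow for.

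Validity, the primary endpoint and N = 112 are unaffected. The change is worth making because it costs nothing, not because the plan fails without it.

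**What to change.** - In sections 7.2 and 10.1, define hospital stay for the between-arm comparison as days from randomisation to discharge, in both arms. Define ICU stay the same way for consistency.
- Move the interval between entering hospital and entering the ICU from the outcome list in section 7.2 to the baseline characteristics in section 7.1.
- Report whole hospital and ICU stay descriptively by arm.
- Reconcile sections 5.1 and 5.3 on patients already in the ICU when shock begins, so that it is clear whether pre-randomisation ICU days can arise.

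The cost is wording. Section 7.1 already collects the hospital admission date and the ICU admission date and time, and it times baseline laboratory tests relative to randomisation, so that time has to be known. No new data and no change to the sample size are needed. The definition should be fixed before any comparison by arm is seen.
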